5.3 Lifestyle Considerations

Not applicable

5.4 Screen Failures

Screen failures are defined as study participants whom parent/legal guardian consented to participate in the clinical trial but are not subsequently randomly assigned to the study drug. A minimal set of screen failure information is required to ensure transparent reporting of screen failure participants, to meet the Consolidated Standards of Reporting Trials (CONSORT) publishing requirements and to respond to queries from regulatory authorities. Minimal information includes demography, screen failure details, eligibility criteria, and any serious adverse event (SAE).

Individuals who do not meet the criteria for participation in this trial (screen failure) MAY NOT be rescreened.

5.5 Strategies for Recruitment and Retention

5.5.1 Target Study Sample Size

Literature supports that lower loading doses of phenobarbital achieve seizure control in approximately 30 to 60% of treated neonates, with higher loading doses achieving seizure control up to 85% (19, 20, 23, 24). Based on 70% and 50% of study participants would achieve seizure control in high dose and low, respectively, an effect size of 20%, an alpha of 0.05 and 80% power, it is estimated that the number of completed study participants required will be 93 study participants in each group (total 186). With approximately, 5% dropout and or non-evaluable study participants, the minimum required for randomization will be 196. A screen failure rate of approximately 60% is anticipated. A total of 490 study participants would be enrolled.

5.5.2 Anticipated Accrual Rate

It is estimated that investigator sites will enroll approximately 1-2 neonates a month. This rate would achieve the necessary 490 screened over the course of approximately one year.

5.5.3 Anticipated Number of Sites

Total number of sites/institutions expected to enroll study participants is up to 30 sites.

5.5.4 Source of Study Participants

Study participants are expected to come from sites/institutions that are level 3/level 4 NICUs.

5.5.5 Recruitment Venues

Not applicable

5.5.6 Identification of Potential Study Participants

Maternity ward and hospital transfer staff will, at minimum, be informed about the study being performed at their associated NICU. The ward or transfer staff will alert the PI or delegated study staff of the transfer of the potential study participant after their birth. The ward staff should inform the study staff of the potential seizure risk, any suspected seizure activity and who identified the seizure risk/activity. At that time, it will be the responsibility of the PI or designated study staff to begin the informed consent process with the parents/legal guardians as well as ensure ward or transfer staff do not administer any prohibited anticonvulsants.

Potential study participants who are at increased risk of seizure activity are listed below. The list is not all inclusive and can be used as a guide when determining study participant eligibility.

Study participants with the following characteristics may be high risk for experiencing seizures:

- Hypoxic-ischemic encephalopathy
- Ischemic stroke
- Intracranial hemorrhage
- Epileptic encephalopathy
- Intracranial infection

Those with the following characteristics are recommended to not be included, but ultimately at the discretion of the investigator and are within the study participant eligibility requirements.

- Brain malformation
- Transient metabolic (e.g. hypoglycemia, hypocalcemia)
- Benign familial epilepsy

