2.1 Study Rationale

This is a randomized, double-blind, parallel-group, phase 3 study to evaluate the efficacy of the administration of phenobarbital sodium injection in neonates who have suffered from electrographic or electroclinical seizure. As neonatal seizures can have long-term adverse effects, including death, placebo-controlled studies are not appropriate for this population. This study is designed to show intravenous phenobarbital is effective at preventing subsequent seizures by demonstrating greater efficacy at a higher dose compared to a lower dose.

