However, phenobarbital remains the first-line therapy for acute seizures in neonates in the USA and international survey data indicate that it remains the most commonly used agent in this setting ⁽²⁾. Seizures occur more often during the newborn period (2-3.5 per 1000 live births) than at any later age. Neonatal seizures can lead to frequent and serious long-term consequences in survivors, such as later epilepsy and significant cognitive and motor disabilities. A National Hospital Discharge Survey indicates that the incidence of all types of neonatal seizures is 2.84 per 1,000 live births in the United States; similar rates of neonatal seizures have been reported in population-based studies in California (0.95/1000 live births) and Texas (1.8/1000 live births) ⁽³⁻⁵⁾. For

hypoxic-ischemic encephalopathy specifically, similar incidence rates of 1-3 per 1000 live births have been reported in the United States and other high-income countries (6, 7). In a recent Task Force Report for the ILAE Commission of Pediatrics, phenobarbital, carbamazepine, and valproate were recommended choices for benign infantile convulsions, but the committee indicated that each was “possibly effective” and that the published data were “weak” with overall recommendations of “C” (possibly effective, ineffective, or harmful, or as useful/predictive or not useful/predictive) for all three drugs according to the American Academy of Neurology (AAN) grading system (8).

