4.1 Overall Design

This is a multicenter, randomized, double-blinded, active-controlled, parallel study in neonates (defined as ≥ 34 - ≤ 44 gestational weeks). The study will consist of a Screening Period, Double-Blind Treatment Period, Follow-up Period and an Open-Label Extension Period. The study participant population is neonates being admitted to the NICU and requiring continuous video electroencephalography (cvEEG) for seizure detection. One or two parents and/or legal guardians must provide written approval of informed consent, before the neonate can be assessed, monitored and managed in accordance with the study protocol and before any study data can be collected and recorded as study data. The reviewing IRB, based on its standard operating procedures, will determine number of parents/legal guardians who will be required to sign the informed consent.

Upon NICU admission and after parents or legal guardians provide informed consent, neonates will be monitored for electrographic seizures.

Seizures requiring study drug treatment will be defined as cumulative electrographic seizure of at least 30 sec/h (22). Confirmation of electrographic seizures by principal investigator or site designees (recommended to be a pediatric neurologist and/or neurophysiologist) is required. Randomization and study drug administration should start as soon as possible after the 30 sec/h of seizure activity criteria is met ideally within 30 min (maximum two hours) (22). If study drug cannot be administered within two hours of recognition of qualifying seizure burden (≥ 30 sec/h), then study drug should not be administered and the neonate will be discontinued from the study and will be a screen failure.

Following confirmation of seizure criteria, neonates will be randomized in a 1:1 allocation to receive a phenobarbital treatment loading dose of 20mg/kg or 40mg/kg, infused over 30 minutes.

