A population pharmacokinetic approach will be implemented using sparse sampling collection. Collection of plasma samples for phenobarbital analysis will be obtained after each loading dose and will follow the sampling guidelines in the schedule of activities (Section 1.3). Additional plasma samples will be obtained at the completion of the treatment period or at early study discontinuation. In order to maintain the study blind, the phenobarbital plasma concentrations will not be made available to the study personnel.

Seizure management in the treatment period will be determined by cvEEG monitoring. Recording of all vital signs and collection of laboratory safety monitoring and collection of phenobarbital plasma samples will be dependent on the clinical management and status of the neonate. The principal investigator will be allowed to discontinue the neonate from the study protocol at any time throughout the study protocol and allowed to administer alternative anticonvulsant therapy as medically required or following standard of care guidelines.

The study treatment period for the primary study analysis will end 24 hours after the neonate meets the seizure criteria and receives the initial phenobarbital study dose (i.e. T0-24 hr). Prior to completing the Treatment Period or early study discontinuation, cvEEG assessment, clinical seizure assessment, and vital signs will be recorded, clinical laboratory tests will be performed, and a phenobarbital plasma sample will be collected. The neonate will be monitored for an additional 24 hours (Follow-up Period) after the Treatment Period is completed. During the 24-hour Follow-up Period general seizure activity, administration of additional non-study anticonvulsant medication, and adverse events will be recorded. Neonates requiring ongoing/maintenance intravenous phenobarbital therapy following study treatment completion will enter an Open Label Extension Period (up to 3 days) and will be monitored for safety and additional phenobarbital plasma samples will be obtained while they are on therapy and until hospital discharge. All study related assessments and work related to the study will be compensated by the funding Sponsor.

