4.2 Scientific Rationale for Study Design

4.3 Justification for Dose

The clinical management of neonatal seizures and the doses (both partial and cumulative) of phenobarbital administered as first line therapy have generally varied among clinicians and institutions. A total daily dose up to 50 mg/kg have been recommended for the treatment of neonatal seizures (12). Based on the published literature and current standard practices, the most frequently used initial doses of phenobarbital to treat neonatal HIE are 20 to 30 mg/kg i.v. followed by maintenance dose of 4 to 6 mg/kg per day (2). If seizures do not resolve with the initial dose, repeat boluses of 10 to 20 mg/kg may be administered with a goal of approximately 50 µg/mL phenobarbital serum level or a total 24 hour total dose of 50 mg/kg (2).

The Sponsor proposes evaluating two double-blind intravenous dose regimens of phenobarbital: Phenobarbital 20 mg/kg (initial dose) followed by 20 mg/kg (second dose, if required) [total daily dose 40 mg/kg] or phenobarbital 40 mg/kg (initial dose) followed by 10 mg/kg (second dose, if required)[total daily dose of 50 mg/kg].

If seizures do not resolve following the initial or second dose of phenobarbital, the PI or site designee will choose an alternate drug for additional dosing. The PI or site designee will be permitted to choose an alternate drug of choice if the neonate does not achieve appropriate seizure control at any time during the study.

For ethical concerns, there will not be a placebo control group.

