5.2 Exclusion Criteria

An individual who meets any of the following criteria will be excluded from participation in this study:

1. Received anticonvulsant treatment, including phenobarbital, prior to randomization (with exception of lorazepam and midazolam administered ≥ 8 hours before enrollment)
2. Strong suspicion or confirmed diagnosis of brain malformation, inborn error of metabolism genetic syndrome, or major congenital malformation prior to randomization

3. Seizures responding to correction of hypoglycemia, hypocalcemia or any other metabolic disorder
4. Death appears to be imminent as assessed by the NICU attending physician
5. Is currently enrolled in another study assessing the same and/or similar primary/secondary endpoints with/without drug treatment.

Study participants who may be already participating in another neonatal clinical trial (e.g., registry or observational) that meet all MI-5780 inclusion criteria and none of the MI-5780 exclusion criteria as well as can meet study assessment requirements, can be enrolled into this study. In addition, study participants enrolled in this trial can enroll in other neonatal trials as long as 1) the inclusion criteria for study MI-5780 continue to be met 2) none of the exclusion criteria for study MI-5780 are met 3) the other study will not result in minor or major MI-5780 protocol deviations.

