6.5 Concomitant Therapy

6.5.1 Allowed Concomitant Medication

For this protocol, a prescription medication is defined as a medication that can be prescribed only by a properly authorized/licensed clinician. Medications to be reported in the Case Report Form (CRF) are concomitant prescription medications, over-the-counter medications (if applicable) and supplements (if applicable).

Only the short acting benzodiazepine lorazepam and midazolam administered ≥ 8 hours before enrollment will be permitted prior to study entry.

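### Protocol 5.5.6 has study staff ensure that no disqualifying anticonvulsant is given while consent is only being started, with no exception for clinically indicated treatment

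*Protocol*

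**What the plan says.** Protocol 5.5.6 describes how candidates are found. Ward or transfer staff alert the study team and report seizure risk, any suspected seizure activity, and who identified it. At that point the investigator or study staff are to "begin the informed consent process with the parents/legal guardians as well as ensure ward or transfer staff do not administer any prohibited anticonvulsants". Both duties start together, so the second applies before a parent has agreed to anything.

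Section 5.5.6 does not list the prohibited drugs. The eligibility rules supply the list:

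- Exclusion criterion 1 (5.2) rules out a neonate who "Received anticonvulsant treatment, including phenobarbital, prior to randomization", except for lorazepam or midazolam given at least 8 hours before enrollment.
- Section 6.5.1 repeats that limit for the period before study entry: "Only the short acting benzodiazepine lorazepam and midazolam administered" at least 8 hours before enrollment is allowed.

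Section 2.2 states that "phenobarbital remains the first-line therapy for acute seizures in neonates in the USA".

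**The concern.** The drug most likely to be ordered for a neonate with acute seizures is the one that exclusion 1 names as disqualifying. A benzodiazepine given around the time of the alert also disqualifies, unless 8 hours then pass before enrollment. An instruction to *ensure* that such drugs are not given, with nothing said about clinical need, can be followed by holding treatment back so that the neonate stays eligible.

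At stake is the care of an infant whose parents have not yet consented. The protocol takes untreated seizures seriously: section 2.1 rejects a placebo arm on the ground that "As neonatal seizures can have long-term adverse effects, including death, placebo-controlled studies are not appropriate for this population". The same reasoning argues against leaving indicated treatment before consent unprotected.

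**Working it through.** No arithmetic applies. The documents give no figure for this point, so the check sets the relevant provisions side by side.

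**1. When the duty starts.** Under 5.5.6 it starts at the alert, when the consent process is only being begun. The report may already include suspected seizure activity.

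**2. What it covers.** The scope is inferred from 5.2 and 6.5.1, because 5.5.6 gives no definition. On the protocol's wording it covers phenobarbital and every other anticonvulsant, and lorazepam or midazolam inside the 8-hour limit. SAP 3.3.2 restates exclusion 1 without the benzodiazepine exception; the protocol's version is used here.

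**3. Whether any provision protects indicated treatment in this window.**

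| Provision | What it gives | Does it reach the window before consent? |
|---|---|---|
| Protocol 4.1 | The investigator may discontinue the neonate and is "allowed to administer alternative anticonvulsant therapy as medically required or following standard of care guidelines" | No. It is written for neonates in the study. |
| Protocol 4.3 | The investigator or site designee is "permitted to choose an alternate drug of choice if the neonate does not achieve appropriate seizure control at any time during the study" | No. It is also written for neonates in the study. |
| Protocol 10.1.1.2 | Care does not suffer if parents decline | No. It concerns refusal, not parents who have yet to decide. |
| Protocol 5.1 and 10.1.1.1 | Remote consent; IRB-approved verbal consent to start screening | Only in part. They shorten the window but do not close it. |
| Protocol 4.1, dosing clock | Study drug ideally within 30 minutes, at most two hours | No. It runs from recognition of qualifying seizure burden; no limit is set for the time before consent. |
| Statement of Compliance; Appendix II | GCP, 45 CFR 46, Declaration of Helsinki | Only as general commitments. They do not qualify this instruction. |

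None of these is an exception for clinically indicated treatment before consent.

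**4. How many neonates could be affected.** The documents do not say how many are reported before consent, how many of those need treatment, or how long consent takes. No number follows.

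**5. Effect on the comparison.** The clause acts before randomization, when no arm has been assigned. It cannot act differently on the two dose groups. The sample size and the analysis do not depend on it.

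**The case against.** The strongest answer is that 5.5.6 is a recruitment section and the clause asks only for liaison: make sure that ward staff do not inadvertently give a disqualifying drug. Nothing in it says to withhold or delay indicated treatment, and nothing gives study staff authority over the ward clinicians. This reading is possible, and it is why the harm is stated conditionally. It does not settle the matter. Section 5.5.6 already says separately that ward and transfer staff are told about the study, and the verb in this clause is stronger than *inform*.

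The group at risk is also narrower than all reported neonates. The trigger includes mere seizure risk and unconfirmed events, for which section 8.2.8 points to cvEEG. Section 2.2 calls phenobarbital first-line for acute seizures, not for risk. A neonate given lorazepam or midazolam can still be enrolled once 8 hours have passed. All of this stands.

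The Recruitment Plan (5.5.7, 5.5.8) and the Operational Procedure Manual may contain an exception. They are not available here, and a protocol instruction should be safe to follow without them.

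Three stronger readings are tempting, and the documents do not support them:

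- **A direct conflict with 4.1.** That section says that parents or guardians "must provide written approval of informed consent, before the neonate can be assessed, monitored and managed in accordance with the study protocol". A reader might infer that 5.5.6 breaks this rule. That follows only if speaking to ward staff counts as managing the neonate under the protocol, which the text does not say.
- **A size taken from the screen failures.** Section 5.5.1 anticipates about 60% screen failures. Section 5.4 counts only neonates whose parents consented, so this figure cannot measure a problem that arises before consent.
- **A problem wholly invisible in the trial's records.** Reportable events start after consent (8.3.4). But for neonates later consented, the prior-medication review (1.3, 4.1.2) and medical history (8.2.1) would show some of what happened earlier. Only neonates never consented would be invisible.

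**Conclusion.** The point holds as a matter of protocol wording and patient safety. Section 5.5.6 states an instruction that, followed literally, could lead to indicated treatment being held back for eligibility before a parent has agreed, and neither document excepts that case. It should be corrected.

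The conclusion rests on two assumptions: that the prohibited drugs are those defined by 5.2 and 6.5.1, and that no unseen manual already supplies the exception. Confidence is medium, because the liaison reading is open. The number of neonates affected cannot be derived. The comparison between arms is unaffected. Nothing in the documents shows that treatment has been withheld or that the sponsor intends it.

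**What to change.** In Protocol 5.5.6, keep the duty to begin the consent process and replace the rest of the clause with:

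> and inform ward and transfer staff of the eligibility criteria. Clinically indicated anticonvulsant treatment must not be withheld or delayed to preserve study eligibility. A neonate so treated before randomization is ineligible under exclusion criterion 1, unless the lorazepam/midazolam exception applies.

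The safeguard deliberately has no time limit. If it were confined to the period before consent, it could imply that withholding for eligibility is acceptable between consent and randomization, a screening period of up to 24 hours (4.1.2).

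The change is one clause. Exclusion criterion 1, the sample size and the analysis stay as they are. The downside is accrual: some additional neonates will be treated first and so become ineligible. The documents do not give the rate, and because phenobarbital is first-line the loss may not be negligible. If the sponsor already intends the liaison reading, the new wording only states that intention.

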5.5.7 Recruitment Strategies

Specific recruitment strategies are detailed in a separate Recruitment Plan.

5.5.8 Long-term Recruitment/Enrollment Strategies

Specific recruitment strategies are detailed in a separate Recruitment Plan.

5.5.9 Justification for Vulnerable Population Recruitment

Phenobarbital is the first line therapy for neonatal seizures. In order to evaluate the efficacy of phenobarbital in a randomized, double-blind clinical trial, neonates must be included as the study population. The risks associated with enrollment are discussed in [Section 2.3](#).

5.5.10 Compensation for Study Participation

Study participants' parents/legal guardians will not be receiving compensation for participating in the study. This information will be clearly outlined and described in the informed consent form and approved by an institutional review board (IRB).

6 Study Drug

6.1 Study Drug(s) Administration

6.1.1 Study Drug Description

Phenobarbital sodium injection is part of the class of drugs known as barbiturates. The barbiturates are nonselective central nervous system (CNS) depressants which are primarily used as sedative hypnotics and anticonvulsants in subhypnotic doses. The barbiturates and their sodium salts are subject to control under the Federal Controlled Substances Act as scheduled IV controlled substances.

Barbiturates are substituted pyrimidine derivatives in which the basic structure common to these drugs is barbituric acid, a substance which has no central nervous system activity. CNS activity is obtained by substituting alkyl, alkenyl or aryl groups on the pyrimidine ring.

6.1.2 Dosing and Administration

Following confirmation of seizure criteria, neonates will receive 1 of 2 different phenobarbital treatment dose regimens.

- Phenobarbital 20 mg/kg (first/initial dose) followed by 20 mg/kg (if required)[dose to be prepared from 90 mg/ml vials], or
- Phenobarbital 40 mg/kg (first/initial dose) followed by 10 mg/kg (if required)[dose to be prepared from 90 mg/ml vials]

The initial dose will be administered intravenously over a 30-minute period. If seizures persist and the criteria for a second dose is achieved, a second dose of phenobarbital will be administered.

The time period between the first and second dose of phenobarbital cannot occur within 30 minutes of the end of the first dose. Note: the second loading dose can only be administered while study participant is in the Treatment Period and cannot be administered during the Follow-up Period.

Any additional treatment required must be a second line anticonvulsant and be based on site/institutional protocol/standard operating procedures.

If seizures persist following the second dose of phenobarbital, additional treatment will be based on site/institutional protocol/standard operating procedures or site has the option to administer the phenobarbital maintenance dose. Note, the optional maintenance dose cannot be administered during the Treatment Period. Study participant must enter the Follow-up Period before phenobarbital maintenance dose can be administered.

If study participant qualifies for the optional phenobarbital maintenance dose, the study participant can enter the Open-Label Extension Period.

- Optional Maintenance Dose: 5 mg/kg/day administered intravenously as a single dose over a 30-minute period, no earlier than 24 hours after completion of initial loading dose (dose to be prepared from 55 mg/ml vials)

Treatment administration information should be reported to the study participants treating pediatric physician and entered into their medical records at time of study completion and unblinding of the study participant.

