4.4 End of Study Definition

A study participant is considered to have completed the study if he or she has completed all phases of the study including the last scheduled procedure prior to discharge shown in the Schedule of Activities (SoA).

The end of the study is defined as completion of the last procedure shown in the SoA in the trial for the last enrolled study participant.

5 Study Population

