6.3.1 Unblinding

The Investigator may unblind an individual study participant's treatment in an emergency when knowledge of such treatment may have an impact on further treatment decisions or aid in the emergency treatment of the study participant. Every effort must be made to contact the Medical Monitor prior to any unblinding of the study drug. The circumstances that lead to unblinding will be promptly communicated via telephone and in writing to the Medical Monitor.

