8.3.4 Time Period and Frequency for Event Assessment and Follow-up

The occurrence of an adverse event (AE) or serious adverse event (SAE) may come to the attention of study personnel during study visits and interviews of a study participant presenting for medical care, or upon review by a study monitor.

All AEs including local and systemic reactions not meeting the criteria for SAEs will be captured on the appropriate case report form (CRF). Information to be collected includes event description, time of onset, clinician's assessment of severity, relationship to study product (assessed only by those with the training and authority to make a diagnosis), and time of resolution/stabilization of the event. All AEs occurring while on study must be documented appropriately regardless of relationship. All AEs will be followed to adequate resolution.

Any medical condition that is present at the time that the participant is screened will be considered as baseline and not reported as an AE. However, if the study participant's condition deteriorates at any time during the study, it will be recorded as an AE.

Changes in the severity of an AE will be documented to allow an assessment of the duration of the event at each level of severity to be performed. AEs characterized as intermittent require documentation of onset and duration of each episode.

PI will record all reportable events with start dates occurring any time after informed consent is obtained until 7 (for non-serious AEs) or 30 days (for SAEs) after the last day of study participation. A follow-up call at day 7 or day 30 will be conducted to confirm resolution or stabilization of adverse events. At each study visit, the investigator will inquire about the occurrence of AE/SAEs since the last visit. Events will be followed for outcome information until resolution or stabilization.

Any adverse event or abnormal laboratory result considered clinically relevant will be followed until it reaches a satisfactory resolution, becomes stable, or can be explained by other causes (e.g., concurrent condition or medication), and clinical judgment indicates that further evaluation is not warranted. All findings must be reported in the study participant's file.

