10.1.8 Clinical Monitoring

Clinical site monitoring is conducted to ensure that the rights and well-being of trial study participants are protected, that the reported trial data are accurate, complete, and verifiable, and that the conduct of the trial is in compliance with the currently approved protocol/amendment(s), Clinical Monitoring Plan (CMP), with International Conference on Harmonization Good Clinical Practice (ICH GCP), and with applicable regulatory requirement(s).

- Monitoring for this study will be performed by trained NEMA Clinical Research Associates.
- Monitoring will be done on-site and remotely. Frequency of visits will be based on guidelines set forth in the CMP. 100% Source Document Verification will be performed.
- Sponsor will be provided copies of monitoring reports within 30 days of visit.
- Details of clinical site monitoring are documented in a Clinical Monitoring Plan (CMP). The CMP describes in detail who will conduct the monitoring, at what frequency monitoring will be done, at what level of detail monitoring will be performed, and the distribution of monitoring reports.
- Independent audits will be conducted by NEMA Quality Manager or Designee to ensure monitoring practices are performed consistently across all participating sites and that monitors are following the CMP.

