3.4. Randomisation

Subjects will be assigned unique subject numbers upon completion of the Screening Period and upon achieving the seizure criteria.

CONFIDENTIAL

A unique randomization number will be assigned by an interactive web response system (IWRS) once eligibility for the Treatment Period of the study has been determined. A permuted block randomization list will be prepared by an external-to-study, unblinded biostatistician.

Detailed instructions for contacting the IWRS will be provided in the Study Manual. The PI or designee will use the IWRS to determine which IMP will be dispensed to a given subject for the Treatment Period of the study. The unblinded investigational pharmacist will prepare the IMP and provide to the PI or designee for administration.

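### Protocol 6.1.2 can be read as disclosing each neonate's dose arm at that neonate's own completion, and neither document says when routine unblinding takes place

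*Protocol*

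**What the plan says.** Protocol 6.1.2 closes with an instruction on disclosure: "Treatment administration information should be reported to the study participants treating pediatric physician". The same sentence has the information "entered into their medical records at time of study completion and unblinding of the study participant". It does not use the word allocation, but because the step is tied to unblinding, the information must reveal the dose arm.

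The only unblinding procedure in the protocol is in 6.3.1: "The Investigator may unblind an individual study participant's treatment in an emergency when knowledge of such treatment may have an impact on further treatment decisions". SAP 3.5 repeats it. Neither document describes a routine unblinding, its date relative to database lock, or who carries it out.

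Protocol 4.4 defines completion for the individual: "A study participant is considered to have completed the study if he or she has completed all phases of the study". It defines the end of the study separately, by the last enrolled participant. The synopsis gives up to 5 days for one neonate.

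On what follows participation, 8.3.4 has events recorded "until 7 (for non-serious AEs) or 30 days (for SAEs) after the last day of study participation", and 8.3.3.1 gives causality to the clinician who examines the participant. Section 10.1.8 adds that "100% Source Document Verification will be performed". On allocation, SAP 3.4 says that "A permuted block randomization list will be prepared"; block size is not given.

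**The concern.** A site reading 6.1.2 next to 4.4 could reasonably disclose each neonate's arm when that neonate finishes, within days of dosing. Three things would then be exposed.

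- **Safety by dose.** Protocol 3.1.1 puts safety as well as efficacy by dose in the primary objective. Severity and causality of later events could be judged by clinicians who can see the dose in the chart.
- **Monitoring before lock.** Monitors verifying every source document would meet the allocation while queries are still open.
- **Concealment of later allocations.** Sites that accumulate known allocations from a permuted-block list can partly anticipate the next one. The same staff confirm qualifying seizures and decide on further treatment, which is what the primary endpoint counts.

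The protocol otherwise guards the blind with care. It blinds all study personnel except the pharmacist (4.1, 6.2.4), withholds plasma concentrations (4.1), and describes the DSMB as the sole unblinded party (7.4.1.2). Disclosure neonate by neonate would undo that.

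**Working it through.** No figure in the plan settles this. The question is what the text says, so the texts come first and the arithmetic only sizes the consequence.

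**1. Which completion is meant?**
- For the participant level: 4.4 uses completing the study for one neonate and a different term for the trial; 6.1.2 speaks of unblinding one study participant, in the singular.
- For the trial level: the synopsis gives an estimated study completion date of Q4 2023; 10.1.4 uses completion of the study for the whole trial; the blinding statements in 4.1, 6.2.4 and 7.4.1.2 fit disclosure after the trial.
- Result: usage is mixed, and 6.1.2 does not choose.

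**2. Is there a routine unblinding for 6.1.2 to refer to?** Protocol 6.3.1 and SAP 3.5 cover emergencies. No other section describes unblinding of participants. Result: 6.1.2 relies on an event that is nowhere defined, under either reading.

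**3. Timing under the participant-level reading.** Inputs: participation up to 5 days (synopsis); recording for 7 and 30 days afterwards (8.3.4); accrual of about one year (5.5.2).
- If disclosure falls on day 5, non-serious events are recorded to day 5 + 7 = 12 and serious events to day 5 + 30 = 35, all after disclosure.
- With uniform accrual over 365 days (assumed), the share disclosed before enrolment closes is 1 − 5/365 = 98.6%.

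**4. Predictability under the participant-level reading.** Inputs: 1:1 allocation (4.1) and permuted blocks (SAP 3.4). Assumptions: staff know every earlier allocation in the block and guess the arm with more places left. Block sizes are assumed.
- Block of 4, chance of a correct guess by position: 1/2, 2/3, 2/3, 1. Mean = 2.833/4 = 0.708. Known with certainty: (1/3 + 1)/4 = 0.333.
- Block of 6: 0.5, 0.6, 0.6, 0.7, 0.7, 1. Mean = 4.1/6 = 0.683. Known with certainty: (0.1 + 0.4 + 1)/6 = 0.25.
- Blocks of 2 and 8 give 0.75 and 0.67. Under concealment the value is 0.50.

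These are means over completed blocks. SAP 5.3 calls HIE and seizure burden stratification factors, which would make four strata. The plan's number randomized reproduces: 186/0.95 = 195.8, so 196. With up to 30 sites (5.5.3), 196/30 is about 6.5 neonates per site and 6.5/4 about 1.6 per site and stratum. If blocks ran within both, most would not get past their second position. The mean over the first two positions is (0.50 + 0.667)/2 = 0.58 for blocks of 4 and (0.50 + 0.60)/2 = 0.55 for blocks of 6. Fewer sites would raise this; central blocks would lower it.

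**5. The neonate's own efficacy outcome.** The primary endpoint ends at 24 hours. Completion under 4.4 needs all phases, including follow-up to 48 hours, so disclosure at completion comes after it.

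**The case against.** The strongest reply is that 6.1.2 merely says when information is passed on once unblinding has occurred, and that trial-level unblinding is the reading that agrees with every other blinding statement. That is a fair reading, and it rules out several stronger claims that a reader might infer.

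- *That the protocol orders disclosure while the trial is enrolling.* No sentence says so; it follows only if completion is taken at participant level.
- *That 6.3.1 forbids any other unblinding, so the sections contradict each other.* Section 6.3.1 permits emergency unblinding and is silent on the rest. This is a gap, not a contradiction.
- *That staff could guess about 70% of allocations.* This needs the participant-level reading, the assumed block sizes, completed blocks at the site, and staff who track the charts.
- *That all later adverse events would be judged unblinded.* This needs disclosure on the last day and assessors who read it. The named recipient is the treating physician, and the documents do not say that this person assesses events.

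What the reply does not remove is the ambiguity. A site has to act on the sentence, 4.4 points it towards the neonate's own completion, and no section corrects it.

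There is also a care argument for early disclosure: 8.2.7.1 reports a half-life of about 114 hours, so the treating physician may want the dose soon after discharge. That is a real cost of waiting, and it is why the emergency route must stay open.

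**Conclusion.** The point holds as an ambiguity that should be closed. Protocol 6.1.2 can be read as disclosing the arm at each neonate's completion, and the routine unblinding that it presupposes is undefined in both documents.

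If a site applied that reading, about 99% of neonates would be disclosed before enrolment closed (uniform accrual over one year, 5-day participation). The 7-day and 30-day recording periods could then run with the dose known. This possible bias in safety by dose is the main harm, and it does not depend on block design; the documents give no basis for its direction or size.

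Predictability of later allocations is secondary. It ranges from little, with central blocks, through 55 to 58% over the first two positions within site and stratum, to 68 to 71% over completed blocks of 6 or 4. Under the trial-level reading, none of these consequences arises.

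**What to change.** Reword the last sentence of 6.1.2 so that routine disclosure of the assigned arm to the treating physician and the medical record takes place after database lock and trial-level unblinding, with any earlier disclosure only through the emergency route in 6.3.1. State who releases the information. Reconcile the wording with 4.1, 4.4 and 7.4.1.2, and add the routine unblinding step to SAP 3.5 so that the two documents agree.

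The cost is one protocol sentence and its SAP counterpart. The downside is that the treating physician learns the arm later, with emergency unblinding still available. No dose, schedule or clinical rule changes. If trial-level timing was always intended, the edit simply records it.
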